8.1.1 Study Design

Figure 1 Flow Chart of the Study

CONFIDENTIAL

8.1.2 Schedule of Assessments

Period	Screening Period	Double-blind Acute Treatment Period							Double-blind Down Taper Period	Follow-up
Visit	1	2	3	4	5	6	7/ET ^a	8 ^b	Telephone Contact	
Day/Week	Day -21 to -1	Baseline Day 1	Week 1 ^c	Week 2 ^c	Week 4 ^c	Week 6 ^c	Week 8/ET ^c	Week 9 ^c	Week 10 ^c	
Subject Informed Consent/Assent	X									
Parent Informed Consent	X									
Inclusion/Exclusion Criteria	X	X								
Demographics	X									
Medical History	X									
Psychiatric History	X									
Medication History	X									
MINI Kid	X									
Physical Examination	X							X		
Body Mass Index (BMI)	X				X			X		
Randomization		X								
Vital Signs ^d	X	X	X	X	X	X	X	X		
Electrocardiogram (ECG)	X							X		
Urine Drug Screen	X							X		
Screen for HBsAg, HCVAb, HIV	X									
Clinical Chemistry including Thyroid	X ^e							X		
Hematology	X							X		
Urinalysis	X							X		
Pregnancy Test ^f	X	X						X		
C-SSRS	X	X	X	X	X	X	X	X		
CGAS	X	X	X	X	X	X	X	X		
PARS	X	X		X				X		
CGI-S	X	X		X				X		
Global COVID-19 Impact Assessment ^g	X	X	X	X	X	X	X			
Evaluate for Dose Escalation ^h				X	X					
PK Blood Samples ⁱ					X			X		
Dispense Study Drug		X ^j	X	X	X	X	X	X		
Study Drug Accountability			X	X	X	X	X	X		
Adverse Events			◀-----	-----►						

CONFIDENTIAL

Period	Screening Period	Double-blind Acute Treatment Period							Double-blind Down Taper Period	Follow-up
Visit		1	2	3	4	5	6	7/ET ^a	8 ^b	Telephone Contact
Day/Week	Day -21 to -1 Day 1	Baseline	Week 1 ^c	Week 2 ^c	Week 4 ^c	Week 6 ^c	Week 8/ET ^c	Week 9 ^c	Week 10 ^c	
Concomitant Medications	◀-----►									

Abbreviations: BMI = body mass index; CGAS = Children's Global Assessment Scale; CGI-S = Clinical Global Assessment of Severity; COVID-19 = coronavirus disease 2019; C-SSRS = Columbia-Suicide Severity Rating Scale; ECG = electrocardiogram; ET = End of Treatment; HBsAg = hepatitis B surface antigen; HCVAb = hepatitis C virus antibody; HIV = human immunodeficiency virus; MINI Kid = Mini-International Neuropsychiatric Interview for Children and Adolescents; PARS = Pediatric Anxiety Rating Scale; PK = pharmacokinetic.

^a End of Treatment or Early Withdrawal.

^b If a site becomes aware of any adverse events after study completion (occurring outside of a defined study visit, including any contact up to 30 days after receiving the last dose of study drug), all adverse events reported by the patient or patient representative or observed or otherwise identified by the investigator or other study personnel must be documented.

^c Visit window \pm 3 days. Refer to [Section 8.2.2.1, Table 1](#) for visit windows for safety assessments (physical examination, BMI, vital signs, ECG, urine drug screen, clinical chemistry including thyroid, hematology, urinalysis, pregnancy test) and/or PK assessments missed due to remote visits.

^d Vital signs (blood pressure, pulse rate, temperature, and respiration rate) will be recorded at every visit. Height and weight will be recorded at Visit 1 (Screening), Visit 5 (Week 4), and Visit 7 (Week 8/ET) only.

^e Fasting blood sample.

^f A serum pregnancy test will be performed at Visit 1 (Screening); a urine pregnancy test will be performed at Visit 2 (Baseline) and Visit 7 (Week 8/ET) for females of childbearing potential.

^g To be completed last after all other study assessments.

^h Subjects who can tolerate the current dose of 10 mg/day may have a dose escalation to 20 mg/day at the investigator's discretion taking into account the CGI-S score.

ⁱ For PK blood sampling for assented/consented subjects at Visit 5 (Week 4) and Visit 7 (Week 8/ET), 2 blood samples per subject will be collected at each of these visits for escitalopram and S-demethylcitalopram analysis at the following times: Visit 5 (Week 4): for subjects receiving dose in the morning, at 0 h (predose) and \geq 1 h postdose and for subjects receiving dose in the evening, 2 samples at random times during the visit (ie, postdose from the dose received the previous evening), collected at least 2 hours apart from each other; and Visit 7 (Week 8/ET): 2 samples at random times during the visit (ie, postdose from the dose received in the morning or the previous evening), collected at least 2 hours apart from each other.

^j Subjects should take their first dose of study drug in clinic.

CONFIDENTIAL

8.1.3 Schedule of Assessments that Can Be Done Remotely

Period	Double-blind Acute Treatment Period						Double-blind Down Taper Period	Follow-up
Visit	2	3	4	5	6	7/ET ^a	8 ^b	Telephone Contact
Day/Week	Baseline Day 1	Week 1 ^c	Week 2 ^c	Week 4 ^c	Week 6 ^c	Week 8/ET ^c	Week 9 ^c	Week 10 ^c
Inclusion/Exclusion Criteria	X							
Randomization	X							
C-SSRS	X	X	X	X	X	X	X	
CGAS	X	X	X	X	X	X		
PARS	X		X			X		
CGI-S	X		X			X		
Global COVID-19 impact assessment ^d	X	X	X	X	X	X	X	
Evaluate for Dose Escalation ^e			X	X				
Dispense Study Drug ^f	X ^g	X	X	X	X	X		
Study Drug Accountability		X	X	X	X	X	X	
Adverse Events	◀-----►-----►							
Concomitant Medications	◀-----►-----►							

Abbreviations: CGAS = Children's Global Assessment Scale; CGI-S = Clinical Global Assessment of Severity; COVID-19 = coronavirus disease 2019; C-SSRS = Columbia-Suicide Severity Rating Scale; ET = End of Treatment; PARS = Pediatric Anxiety Rating Scale; PK = pharmacokinetic.

Notes for Remote Study Visits:

- The Baseline Visit can be remote but it is not preferred. For all female subjects of childbearing potential, the Baseline Visit must take place as an in-clinic visit with all assessments outlined in [Section 8.1.2](#).
- Subject data are collected via telephone or telehealth video calls using a technology provider (see [Appendix 17.3](#)). Sites should remain consistent with either methods (video or telephone) for each subject.
- In-clinic safety and PK assessments missed due to remote visits may be collected per [Section 8.2.2.1, Table 1](#).

^a End of Treatment or Early Withdrawal.

^b If a site becomes aware of any adverse events after study completion (occurring outside of a defined study visit, including any contact up to 30 days after receiving the last dose of study drug), all adverse events reported by the patient or patient representative or observed or otherwise identified by the investigator or other study personnel must be documented.

^c Visit window ± 3 days.

^d To be completed last after all other study assessments.

^e Subjects who can tolerate the current dose of 10 mg/day may have a dose escalation to 20 mg/day at the investigator's discretion taking into account the CGI-S score.

^f For remote visits study drug will be sent to subjects via curbside (preferred) or courier.

^g In case of a remote Baseline Visit, subjects will receive and take their first dose of study drug via curbside (preferred) or they will receive it by courier and take it at home.

CONFIDENTIAL

8.2 Discussion of Study Design

8.2.1 Study Design

This study will be performed in pediatric subjects (aged 7 through 17 years) with GAD in order to assess safety and efficacy in this patient population.

In order to standardize the subject population and to make it as homogeneous as possible, all subjects must meet the DSM-5 criteria for diagnosis of GAD and have at least moderate severity of GAD assessed using standard rating scales. In addition, the randomization schedule will be stratified so that there is treatment balance within the age group and sex group strata.

There is a known placebo effect in this indication⁹ so this study will use a parallel-group design with a placebo-control arm. As some of the endpoints (eg, safety, clinical assessments) are potentially subjective, this study will be performed in a double-blind manner.

Subjects randomized to the escitalopram treatment arm will receive escitalopram at an initial dose of 10 mg/day with the possibility to increase the dose to 20 mg/day after 2 weeks and 4 weeks. The dose can only be increased if the subject tolerates the current dose. Further details on the selection of doses in this study are provided in [Section 8.4.5](#).

A double-blind treatment period of 8 weeks was selected because it is expected to see a treatment effect within this period and the efficacy of escitalopram in the treatment of GAD beyond 8 weeks has not been systematically studied. The study includes a 1-week double-blind down taper period at the End of Treatment to minimize symptoms associated with discontinuation of escitalopram.

Analyses of short-term placebo-controlled trials of antidepressant drugs (SSRIs and others) showed that these drugs increase the risk of suicidal ideation and behavior (suicidality) in children, adolescents, and young adults (aged 18 through 24 years) with MDD and other psychiatric disorders. In order to monitor this, the C-SSRS will be completed at the Screening, Baseline, and each study visit (see [Section 10.1.2.1](#) for further details).

8.2.2 Quality Management and Risk Evaluation

This protocol was evaluated to identify risks to those processes and data that are critical to assure human subject protection and reliability of study results. To mitigate these risks, on-site and remote risk-based monitoring standard operating procedures will be employed to ensure site compliance with International Council for Harmonisation of Technical Requirements for Pharmaceuticals for Human Use (ICH) current Good Clinical Practice (cGCP). Concurrent medical review by the contract research organization represents an integral component of the study's centralized monitoring

CONFIDENTIAL

activities by monitoring subject safety and ensuring scientific integrity of the study data through the assessment of critical study data identified during the risk assessment for the study. Issues identified during on-site or remote monitoring or during medical review that may affect subject safety, data quality and/or the study's scientific integrity will be communicated to the study team triggering increased frequency of site communication until issues are remediated.

8.2.2.1 COVID-19 Specific Processes

To promote subject safety and data quality during the COVID-19 pandemic, the following processes will be implemented:

- Exclusion of subjects whose anxiety is significantly impacted by COVID-19 as assessed by investigator (see [Section 8.3.3](#)).
- Global COVID-19 impact assessment (see [Section 10.1.1.4](#)).
- Visit conduct options allowing remote visits as outlined below:

During remote study visits data are collected via telephone or videoconference (see [Appendix 17.3](#)).

Any clinical assessment (including physical examination, vital signs, urine, or blood tests) necessary as part of evaluation of a reported adverse event (AE) must be performed immediately. If the study site is closed or the subject is unable to travel to the study site, alternate arrangements for in-person clinical assessment should be secured.

Option 1: In-Clinic Visits

This is the preferred option. All study visits are performed as in-clinic visits with all assessments outlined in the Schedule of Assessments in [Section 8.1.2](#).

Option 2: Remote Visits (except Screening for all subjects and Baseline Visit for female subjects of childbearing potential)

This option is only to be used if local guidance and regulations are preventing the site or subject from completing an in-clinic visit. Screening must take place as an in-clinic visit with all assessments outlined in the Schedule of Assessments in [Section 8.1.2](#). The Baseline Visit must take place as an in-clinic visit for all female subjects of childbearing potential with all assessments outlined in the Schedule of Assessments in [Section 8.1.2](#) (including pregnancy test). All other visits can be completed remotely with the assessments outlined in [Section 8.1.3](#).

[Table 1](#) outlines allowed visit windows if a subject comes into the clinic to complete physical examination, body mass index (BMI), vital signs, electrocardiogram (ECG),

CONFIDENTIAL

urine drug screen, safety lab (clinical chemistry including thyroid, hematology, urinalysis), pregnancy test, and/or PK.

All attempts should be made to collect all safety assessments within 6 weeks of the Visit 7 date, if logistically possible.

If a subject is able to switch from remote visits to in-clinic visits, the investigator should contact the study monitor for guidance.

Table 1 Visit Windows for Safety and PK Assessments Missed due to Remote Visits

Visit	Assessment	Limits for allowance of out-of-window collection
Visit 5/Week 4	PK	up to 3 weeks early or late (\pm 21 days) (Section 10.1.3)
	BMI	up to 3 weeks late (+ 21 days)
Visit 7/Week 8 or ET	PK	up to 1 week late (+ 7 days) (Section 10.1.3)
	Clinical chemistry, hematology, urine drug screen	up to 1 week late (+ 7 days)*
	Physical examination, BMI, vital signs, ECG, urinalysis, pregnancy test	up to 1 week late (+ 7 days)*
Visit 8/Week 9	Vital signs	up to 1 week late (+ 7 days)*

Abbreviations: BMI = body mass index; ECG = electrocardiogram; ET = End of Treatment; PK = pharmacokinetic. Note, if subjects cannot do the assessments within these timeframes, it will be noted as missing assessment(s) for that visit. NOTE: PK assessments outside the above visit windows should not be done at all.

* For purposes of including as safety endpoints, these assessments will be included in the safety analysis if collected up to 1 week late. Any safety data collected 8 days to 42 days late will be considered missing for analysis purposes. The 6-week window is allowed to capture any follow-up safety data on the participant and will be noted in the final study report (see also [Section 11.6](#)).

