The coronavirus disease 2019 (COVID-19) pandemic (and any other naming conventions used) developed after this study began and this protocol has been amended to account for study procedures that need to be modified in association with adhering to local safety guidelines or regulations.

[figure not shown]
During the COVID-19 pandemic, remote study visits, in which data are collected via telephone or videoconference, are possible but not preferred. Nearly all scheduled safety assessments, with exception of the Columbia-Suicide Severity Rating Scale (C-SSRS), are not possible by remote visit and must be collected in person via clinic visits. To

CONFIDENTIAL

accommodate changes sites may need to implement during the pandemic, [Section 8.1.2](#) outlines the conduct of study assessments during in-clinic visits, which is the preferred method of conducting the study, while study assessments for remote visits are included in [Section 8.1.3](#).

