10.3 VITAL SIGNS

Descriptive statistics for vital signs (sitting systolic and diastolic blood pressure, pulse rate, respiration rate, temperature, height, weight, BMI, height percentile, weight percentile, and BMI percentile) and their changes from baseline values at each visit and at the end of study will be presented by treatment group. Height, weight and BMI z-scores will be calculated based on Centers for Disease Control (CDC) growth charts. Only subjects with available baseline and at least 1 postbaseline assessment will be included in the summary.

Vital sign values will be considered PCS if they meet both the observed-value criteria and the change-from-baseline criteria listed in Table 10.3–1. The number and percentage of subjects with PCS postbaseline values will be tabulated by treatment group separately. The percentages will be calculated relative to the number of subjects with available baseline and at least 1 postbaseline assessment. The numerator will be the total number of subjects with available baseline values and at least 1 PCS postbaseline value. A supportive listing of subjects with PCS postbaseline values will be provided, including the SID number, study center number, and baseline and all postbaseline (including non-PCS) values.

In addition, a listing of all AEs that occurred in subjects who had PCS postbaseline vital sign values will be provided.

Table 10.3–1. Criteria for Potentially Clinically Significant Vital Signs

		Criteria ^a				
Parameter	Flag	Observ	ed Value	Change From Pageline		
		Age 7-11	Age 12-17	Change From Baseline		
	High	≥ 125	≥ 140	Increase of ≥ 20		

Page 35 of 53

Sitting systolic blood pressure, mm Hg	Low	≤ 85	≤ 90	Decrease of ≥ 20
Sitting diastolic blood	High	≥ 90	≥ 95	Increase of ≥ 15
pressure, mm Hg	Low	≤ 40	≤ 50	Decrease of ≥ 15
C'44'	High	≥ 130	≥ 110	Increase of ≥ 15
Sitting pulse rate, bpm	Low	≤ 55	≤ 45	Decrease of ≥ 15
Waisht les	High	_	_	> 2 deviations above the age-gender mean weight
Weight, kg	Low	_	_	> 2 deviations below the age-gender mean weight

a A post-baseline value is considered potentially clinically significant if it meets both the observed-value and the change-from-baseline criteria.

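### Table 1 gives vital signs no make-up window at Visit 5, so a subject remote at Visits 3-6 can attend on site for PK or BMI with no blood pressure or pulse reading required

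*Protocol*

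**What the plan says.** Protocol 8.1.2, footnote d: "Vital signs (blood pressure, pulse rate, temperature, and respiration rate) will be recorded at every visit". Between first dose and the end of acute treatment that means Visits 3, 4, 5, 6 and 7 (Weeks 1, 2, 4, 6 and 8).

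Protocol 8.1, on remote conduct: "Nearly all scheduled safety assessments, with exception of the Columbia-Suicide Severity Rating Scale (C-SSRS), are not possible by remote visit", and such assessments have to be done in person. The remote schedule in Protocol 8.1.3 accordingly has no vital-signs row.

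Footnote c of Protocol 8.1.2 names vital signs among the assessments whose windows, when missed because of a remote visit, are to be found in Table 1 of Protocol 8.2.2.1. Table 1 contains:
- Visit 5: PK (21 days either side) and BMI, "up to 3 weeks late (+ 21 days)". Nothing else.
- Visit 7: PK and laboratory tests, and a row reading "Physical examination, BMI, vital signs, ECG, urinalysis, pregnancy test", all up to 7 days late.
- Visit 8: vital signs, up to 7 days late.
- Visits 3, 4 and 6: no row.

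The note under the table says that "if subjects cannot do the assessments within these timeframes, it will be noted as missing assessment(s) for that visit".

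SAP 10.3 counts a subject as a PCS case on one qualifying post-baseline value and takes percentages "relative to the number of subjects with available baseline and at least 1 postbaseline assessment". Protocol 11.6.1.2 says the same.

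**The concern.** Footnote c promises a rule for missed vital signs that Table 1 supplies only for the last two visits. The omission shows most at Visit 5. A remote subject may come in for a blood draw or for height and weight, yet the plan does not ask for blood pressure, pulse, temperature or respiration rate at that attendance.

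Safety is part of the primary objective, and the incidence of vital-sign PCS values is a named safety endpoint. The PCS rule takes no account of how many readings a subject contributes: someone measured once carries the same weight in the denominator as someone measured five times, with fewer chances to become a case. The visits affected also include Weeks 2 and 4, when dose escalation is considered.

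**Working it through.** **Which readings are lost.** The in-clinic schedule has five acute-phase readings. A subject remote at Visits 3-6 whose Visit 7 vital signs are obtained has one, so 4 of 5 (80%) are missing. Visit 8 is left out because SAP 10.0 analyses the down-taper period separately.

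**When the Visit 5 attendance can fall.** Counting from Day 29 (SAP 16.1), PK may be drawn on Days 29 − 21 = 8 to 29 + 21 = 50. BMI may be taken late only, so on Days 29 to 50. A visit within ±3 days of schedule can be run as an ordinary in-clinic Visit 5 with vital signs, so the gap concerns attendance outside those days.

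**Which PCS criteria are affected.** SAP Table 10.3-1 covers systolic and diastolic pressure, pulse and weight. Weight is picked up by the Visit 5 BMI row. The PCS gap is therefore in blood pressure and pulse.

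**Size (illustration only).** The documents state no PCS rate and no remote share, so there is no figure to reproduce. Assume a chance p of a PCS value at each reading, independent readings, and a fraction f of subjects remote at all of Visits 3-6 with Visit 7 obtained. With k readings, the chance of being a case is c(k) = 1 − (1 − p)^k. Reported incidence is (1 − f)·c(5) + f·c(1), and the relative shortfall is f × [1 − c(1)/c(5)].

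| p | c(1) | c(5) | 1 − c(1)/c(5) | shortfall, f = 10% | f = 25% | f = 50% |
|---|---|---|---|---|---|---|
| 0.5% | 0.5% | 2.5% | 0.798 | 8.0% | 19.9% | 39.9% |
| 1% | 1.0% | 4.9% | 0.796 | 8.0% | 19.9% | 39.8% |
| 2% | 2.0% | 9.6% | 0.792 | 7.9% | 19.8% | 39.6% |
| 5% | 5.0% | 22.6% | 0.779 | 7.8% | 19.5% | 38.9% |

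At p = 2%, the 9.6% expected in clinic becomes:
- f = 10%: 0.90 × 9.61 + 0.10 × 2.00 = 8.8%
- f = 25%: 0.75 × 9.61 + 0.25 × 2.00 = 7.7%
- f = 50%: 0.50 × 9.61 + 0.50 × 2.00 = 5.8%

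Positive correlation between a subject's readings reduces these shortfalls. In the limit where all five readings agree, c(5) = c(1) and there is none.

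**Between-arm comparison.** Assume 2% per reading in one arm, 1% in the other, and equal f. With f = 0 the ratio is 9.61/4.90 = 1.96 and the difference 4.7 points. With f = 50% the ratio is 5.80/2.95 = 1.97 and the difference 2.9 points.

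**Effect of adding Visit 5.** Two readings give c(2) = 1 − 0.98² = 3.96% at p = 2%. At f = 25%, incidence is 0.75 × 9.61 + 0.25 × 3.96 = 8.2%, against 7.7% without the change and 9.6% in clinic.

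**The case against.** Several points against the concern stand.
- Table 1 does not bring anyone on site. It sets windows for a subject who comes in, remote visits are allowed only where local guidance or regulations prevent attendance, and PK sampling is limited to subjects who assented or consented to it.
- A reader might infer that the missing readings can never be made up. The documents do not say that. Protocol 8.2.2.1 requires in-person vital signs, without delay, when they are needed to evaluate an adverse event; Protocol 9.5 allows unscheduled visits; and nothing forbids a reading at any attendance. SAP 16.3 uses all post-baseline values for PCS, so such readings would count.
- A reader might also infer that PCS incidence is under-counted as a fact, or that the treatment comparison is biased. The first depends on an unknown remote share and rate. For the second, nothing suggests that remote use differs by arm.
- Dose escalation is tied to tolerability and CGI-S, not to a vital-sign threshold, so the timing argument adds little.
- Remote visits will be tabulated by arm and visit (SAP 6.0), and COVID-19 safety subgroup analyses are allowed (SAP 10.0).

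These points do not remove the gap. Readings prompted by an event or a safety concern do not replace routine ones. The request to collect all safety assessments within six weeks is tied to Visit 7, so it cannot supply Weeks 1-6, and Table 1 treats data 8 to 42 days late as missing for analysis. The SAP 6.0 count of assessments missed due to COVID-19 excludes those permitted to be missed off site, so these readings may not appear there.

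**Conclusion.** The concern holds as a minor gap in the plan. Footnote c and Table 1 do not agree on vital signs, and an out-of-window attendance for Visit 5 PK or BMI carries no requirement to take them. A subject remote at Visits 3-6 may have one of five scheduled acute-phase readings unless an adverse event or unscheduled visit prompts another.

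The direction is clear: absolute blood pressure and pulse PCS incidence would tend to be lower than under in-clinic conduct. The size is not known. Under independence, the relative shortfall is about 8% if 10% of subjects are affected and about 40% if half are; it is smaller if readings are correlated. With balanced remote use the between-arm ratio hardly moves, though the absolute difference shrinks.

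**What to change.** Add vital signs (blood pressure, pulse rate, temperature, respiration rate) to the Visit 5 row of Table 1, to be recorded whenever a subject attends on site for Visit 5 PK or BMI. This brings footnote c and Table 1 into line for that visit.

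Assign each reading to an analysis visit by actual study day under SAP 16.1, not automatically to Week 4. The PK window of Days 8 to 50 runs from the SAP's Week 1 window (Days 2-11) to the first day of its Week 8 window (Day 50 onward). No new PCS rule is needed, given SAP 16.3.

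The change recovers one of the four lost readings; Visits 3, 4 and 6 stay without a routine make-up, and Table 1 should say so. The cost is one table row, which can go into a protocol amendment, and a few minutes per subject, including the five-minute seated rest in Protocol 10.1.2.4, at an attendance already taking place.
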